8.2 HIV Viral Load Testing

For participants LWHIV, viral suppression will be assessed for in-clinic and virtual participants. For in-person participants, viral load testing should be done using an FDA-cleared assay with a limit of detection of 40 copies/mL or lower. For virtual participants, capillary (fingerstick) blood will be self-collected on a DBS card and sent for viral load testing at the Central Laboratory, or a laboratory designated by the Central Laboratory.

8.3 Pharmacology

DBS samples for pharmacology testing will be collected throughout the study from both inperson and virtual participants; however, this testing may be limited to a subset of samples. For participants reporting long-acting PrEP, plasma may be used to assess drug concentrations. Procedures for sample processing and shipping are outlined in the study Lab Processing Chart (LPC). The primary pharmacologic assessments will be performed using assays that have been appropriated validated and approved by the Central Laboratory, an external quality assurance group. Interpretation of pharmacologic results, including modeling, will be led by the Central Laboratory and the ATN Laboratory Diagnostics and Mobile Technologies Scientific Leadership Group, in collaboration with other groups, as needed.

8.4 Substance Use

For all participants (in-person and virtual), urine will be collected for substance use testing. The test will use a POC antibody-based methodology, and specific drug class speciation will not be performed.

9. Participant Management

9.1 Participant Tracking and Follow-Up

The SC study staff will reach out to participants at least every month between study visits to check in on how they are doing and obtain any changes in their contact information. Check-ins will be done using the participant's preferred means of contact (e.g., telephone call, email, text message, chat/WhatsApp) as provided on the Contact Information Worksheet.

The following actions will be taken if a participant fails to complete a required study visit:

- The SC study staff will attempt to contact the participant and reschedule the missed visit within the protocol-specified visit window. At least three attempts should be made to reach the participant to reschedule the missed visit.
- Before a participant is deemed lost to follow-up, the SC Project Lead or designee will make every effort to regain contact with the participant using the participant's preferred means of contact. These contact attempts should be documented in the local contact tracking log.
- Should the participant continue to be unreachable and the visit window closes, the study visit will be considered missed. The SC study staff will attempt to reach the participant for their next scheduled study visit when the visit window opens.
- The participant will be considered lost to follow-up if SC staff are unable to contact them for their final Month 12 visit within 6 weeks after the anticipated date.

9.2 Criteria for Premature Discontinuation from Study Intervention and/or the Study

9.2.1 Temporary Discontinuation of Study Intervention

The SC Project Lead or designee will decide whether a participant needs to temporarily discontinue the study intervention per SOC guidelines. Upon deciding to temporarily hold the study intervention, the SC Project Lead or designee will inform the Protocol Team via the QNS of the decision with the rationale for the decision and plan for re-starting administration of the study intervention.

9.2.2 Permanent Discontinuation of Study Intervention

Participants who are permanently discontinued from study intervention (as applicable) due to an AE, whether serious or nonserious, must be followed until the AE is resolved or considered stable (see Section 13).

9.2.3 Premature Discontinuation from the Study

The SC Project Lead has the authority to withdraw any participant at any time if, in their opinion, it would be in the best interest of the participant. They will inform the participant of the study withdrawal and explain the rationale behind it. The reason for the premature discontinuation or failure to provide a reason must be documented by the SC Project Lead and recorded within the EDC system.

Participants will be prematurely discontinued from the study if any of the following occurs:

- The participant withdraws consent;
- The participant develops a new medical condition or experiences a safety event such that continuing study participation is no longer in the best interest of the participant;
- The participant is noncompliant with study procedures; or
- Death of the participant.

Participants may withdraw from study participation at any time for any reason. Should a participant decide to withdraw from study participation, safety-related follow-up will be encouraged, but not mandated. If a participant withdraws consent, no further data collection will occur from the date consent is rescinded. Study data and specimens that have been recorded/collected prior to study discontinuation will be retained for use by the study.

It is possible that experiencing an AE/SAE may necessitate the participant's stopping or pausing the study intervention; any such participants will continue to be followed for safety until the AE/SAE is either resolved or considered stable, as determined by the SC Project Lead or designee. All safety-related follow-up will cease if the participant withdraws consent.

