6.2 Study Intervention Administration

The IMPACT arm consists of 10 sessions (approximately 50 minutes each) delivered over the course of approximately 10 weeks. The eSOC arm consists of two RR intervention sessions described in Section 6.1.

A participant is not required to finish all intervention sessions to complete a follow-up visit; it is acceptable to miss sessions and continue with follow-up visits. However, once the Month 4 visit is conducted, no further intervention sessions can occur.

Following best practices described in the ERIC framework,^[17] a multifaceted training and implementation strategy for interventionists will be used for implementing the IMPACT intervention across sites and formats. A detailed description (including the Working Alliance Inventory-Therapist Report) of the intervention training and ongoing evaluation plan was acknowledged as an exempt sub study (ATN 170 Addendum: Interventionist Training and Evaluation, Study 11201) by Sterling IRB on August 8, 2023.

To enhance and maximize the adoption and accessibility of the IMPACT intervention, the intervention will be implemented in two separate formats: in-person at the selected ATN SCs and virtually, provided by the central research staff at Brown University and UCLA. This will allow for the intervention to be offered to a larger, broader, and more diverse population in terms of geography and physical ability status.

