7.3 On-Study

The following assessments will be performed at Month 4, Month 8, and Month 12. Visit windows are defined in Section 3.2.5 and included in the Schedule of Events in Appendix 1.

If the follow-up visit is split into 2 days, the primary outcome measures and assessments listed in Appendix 2 should **always** be completed on the same day as biospecimen collection. The entire follow-up visit must be completed within 28 days of the initial follow-up encounter.

Please note, if randomized to the intervention arm, a participant is not required to finish all intervention sessions to complete follow-up visits; it is acceptable to miss sessions and continue in follow-up. However, once the Month 4 visit is conducted, no further intervention sessions can occur.

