7.4.1 Assessments for Participants Discontinuing from Study Intervention

• Document reason for study intervention discontinuation.

- Those who request to stop participating in the study intervention will be asked for the reason(s) for stopping, and a subset will be asked to complete an exit interview.
- In addition, the participant will continue to complete all study follow-up visits, unless the participant decides to discontinue participation in the study entirely.

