11.2 Protocol Deviations

A protocol deviation is any noncompliance or unplanned excursion from the approved investigational plan (e.g., protocol, study MOP, ATN MOGO), or ICH GCP guidelines. The noncompliance may be on the part of the participant, the SC Project Lead, or the SC staff. If a deviation occurs, a corrective action plan may need to be developed and implemented promptly by the SC.

For this study, missed assessments due to participant refusal, scheduling issues, difficulties attending the study visit, and related issues will not be considered protocol deviations in order to facilitate retention of participants for later study assessments. These issues will be tracked and reported to the Protocol Team, however.

SC Project Leads must adhere to the investigational plan as detailed in this protocol and associated study materials (e.g., study MOP, forms instructions, user guides) and only deviate from the protocol in order to prevent immediate harm to participants. SC Project Leads will ensure that all staff assisting with the study are adequately trained to perform the study-related duties and functions they have been delegated.

All protocol deviations must be recorded in the source documents and be promptly entered in the EDC system by the SC staff within 3 business days of SC awareness. It is the responsibility of the SC to use continuous vigilance to identify and report protocol deviations as outlined below.

Protocol deviations can be separated into two categories:

- A nonsignificant deviation is a deviation that affects only logistic or administrative aspects of the study and has no substantive effect on the safety or well-being of study participants; does not affect the value of the data collected; and does not result from willful or knowing misconduct on the part of the SC staff.
- A significant deviation is a deviation that affects the scientific design/integrity of the study; affects the rights, safety, or welfare of study participants; changes the risk/benefit ratio; or violates an ethical principle. Significant deviations for this study may include: 1) enrollment violation; 2) informed consent violation; or 3) failure to link distressed participants to care.

All protocol deviations are to be reported to the Protocol Team through the EDC system by SC staff within 3 business days of SC awareness.

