14.3.2 Populations for Analyses

Intent-to-Treat Population

Analyses of primary and secondary endpoints will be conducted in an Intent-to-Treat population that includes all randomization participants. Participants will be analyzed according to the intervention to which they were randomized.

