14.3.3 Analysis of Primary Endpoint

Estimands

The primary analysis of the primary endpoint will compare the rate of distinct acts of CAS over the course of follow-up between the IMPACT intervention arm and the eSOC comparison arm.

For this endpoint, the primary estimand is defined by the following attributes:

- **Intervention condition:** IMPACT intervention versus eSOC including the effects of intervention discontinuation and intake of additional interventions/therapies.
- **Population:** Cisgender YGBSMM as defined by the inclusion criteria to reflect the key population.
- Variable: Number of distinct acts of CAS without the use of a condom or without the protection of prevention-effective PrEP (for participants NLWHIV) or viral suppression (for participants LWHIV) over the course of follow-up.
- Intercurrent events: The following intercurrent events are anticipated:

- Discontinuation of intervention due to any reason
 - Handling strategy: treatment policy (captured through the intervention condition definition)
- Intake of additional interventions/therapies
 - Handling strategy: treatment policy (captured through the intervention condition definition)

Further intercurrent events are not anticipated at this time.

• **Population-level summary:** Rate ratio between intervention conditions

Analysis Models

For the primary endpoint, a marginal Poisson model will be used, with logarithmic link function, common intercept, linear fixed effect for intervention, and accounting for the length of the reporting period for each observation. A Generalized Estimating Equations (GEE) approach will be used to fit the model, assuming an unstructured working correlation structure. Given the possibility of missing data from participants who discontinue the study prior to the Month 12 visit, inverse probability weighting will be incorporated into the modeling procedure; more details will be described in the SAP. Substitute model specifications to be used in the event the primary model does not converge will be described in the SAP.

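### Section 9.2.3 ends study participation for undefined noncompliance, while other sections keep the same people in follow-up, and so puts outcomes that the primary analysis needs at risk

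*Protocol*

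**What the plan says.** Section 9.2.3 of the protocol introduces its list with "Participants will be prematurely discontinued from the study if any of the following occurs". One item on that list is "The participant is noncompliant with study procedures". The wording is mandatory and covers the whole study, not only the intervention. There is no definition, threshold or review step, and Section 10.2 sends the reader to Section 9.2 for individual stopping criteria.

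Elsewhere the protocol says:

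- Section 6.2, on sessions: "it is acceptable to miss sessions and continue with follow-up visits".
- Section 7.3, for the intervention arm: "it is acceptable to miss sessions and continue in follow-up".
- Section 7.4.1, on a person who stops the intervention: "the participant will continue to complete all study follow-up visits, unless the participant decides to discontinue participation in the study entirely".
- Section 9.1: after a missed visit, staff try to reach the participant for the next one.
- Section 11.2: assessments missed through refusal, scheduling and similar problems "will not be considered protocol deviations in order to facilitate retention of participants for later study assessments". They are still tracked and reported.
- Section 3.2.6: retention efforts run for the whole period of participation.

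On the analysis side, Section 14.3.2 defines an intention-to-treat population: "Participants will be analyzed according to the intervention to which they were randomized". Section 14.3.3 applies a treatment-policy strategy to discontinuation of the intervention for any reason.

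**The concern.** A site faced with a randomized participant who skips sessions or a visit has two instructions. Section 9.2.3 says the participant leaves the study. The other sections say follow-up goes on. Different sites can resolve this differently, and nothing in the text decides between them.

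The consequence is statistical. A treatment-policy comparison in all randomized participants needs outcomes from people who adhere poorly. A rule that ends their participation turns obtainable outcomes into missing ones. Section 14.7 handles missing primary data by inverse probability weighting, with two sensitivity analyses; these methods rest on missing at random or missing completely at random. Removal under an undefined criterion, left to each site to interpret, makes missing at random harder to defend, because the reasons for removal may not be in the data.

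**Working it through.** The conflict is textual. The arithmetic only indicates what could be at stake.

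1. **The plan's own attrition figure.** Section 14.2 needs 291 completers (194 + 97) and randomizes 360 (240 + 120) to allow for 20% attrition. Check: 291 / 0.80 = 363.75, so 364 against 360 stated, about 1% apart. In reverse, 360 × 0.80 = 288 (192 + 96), three below 291. The figure reproduces closely, but there is no slack for further loss created by a study rule.

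2. **Power is not the main issue.** The protocol gives no dispersion, so I back-solve one from its inputs, assuming a two-sample comparison of log rates (rate ratio 0.80, two-sided 0.05, 90% power, 97 versus 194): SD = 0.2231 / [(1.960 + 1.282) × √(1/97 + 1/194)] = 0.554. Power is then Φ(0.2231 / [0.554 × √(1/n₁ + 1/n₂)] − 1.960). With 96 versus 192 it is 89.7%. If a further 10% of the IMPACT arm is lost (96 versus 168) it is 88.3%; with a further 20% (96 versus 144) it is 86.4%.

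3. **Who is exposed after randomization.** Sections 3.2.4 and 5.6 place randomization after both risk-reduction sessions. IMPACT has 10 sessions, so 10 − 2 = 8 remain (1 + 6 + 1); eSOC has 2 − 2 = 0. The Month 4, 8 and 12 visits are the same in both arms. Unequal removal through sessions therefore requires a site to count missed sessions as noncompliance, against Sections 6.2 and 7.3.

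4. **Illustrative bias.** Let p_I and p_C be the proportions removed in IMPACT and eSOC, and k the CAS rate of those removed relative to those retained, the same in both arms. Each arm's true mean is its retained mean times 1 + p(k − 1). If only the retained are seen, the apparent ratio equals the true ratio times [1 + p_C(k − 1)] / [1 + p_I(k − 1)]. None of p_I, p_C or k is in the protocol; the values below are assumptions.

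| k | p_I | p_C | Factor | True 1.00 appears as | True 0.80 appears as |
|---|---|---|---|---|---|
| 1.5 | 10% | 2% | 1.01/1.05 = 0.962 | 0.96 | 0.77 |
| 1.5 | 20% | 2% | 1.01/1.10 = 0.918 | 0.92 | 0.73 |
| 2 | 10% | 2% | 1.02/1.10 = 0.927 | 0.93 | 0.74 |
| 2 | 20% | 2% | 1.02/1.20 = 0.850 | 0.85 | 0.68 |

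The factor is 1 if k = 1 or if removal is equal in the two arms, and the bias reverses if k is below 1. The table also assumes that those removed contribute no follow-up data before removal, that they would otherwise have supplied outcomes, and that weighting recovers nothing.

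**The case against.** The strongest reply is that the specific provisions govern the general one. Sections 6.2, 7.3 and 7.4.1 expressly protect people who miss or stop sessions. Section 7, whose title covers visits and procedures, is mostly about assessments and specimens that are the same in both arms. On that reading missed sessions are not noncompliance and the one-arm mechanism closes. This has weight, and it is why the arm imbalance can only be stated conditionally. It does not remove the conflict. The protocol never says that sessions fall outside study procedures, and Appendix 1 lists them in the Schedule of Events. Even on the narrow reading, 9.2.3 still collides with 3.2.6, 9.1 and 11.2 on missed visits and assessments.

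A second reply is that the clause may serve people who drop out early. Those who miss the risk-reduction windows are never randomized (Section 3.2.4) and cannot bias the comparison. That is true, but they already have their own rule, and the 9.2.3 item is not limited to that period.

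Third, a reader might infer that 9.2.3 contradicts the estimand. It does not. The treatment-policy strategy addresses stopping the intervention, whereas leaving the study is a missing-data matter. The protocol provides for missing data through weighting and multiple imputation, and the details of the weight model are left to the SAP.

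Fourth, the bias figures are assumed, and several things would shrink them. Section 9.2.3 keeps data recorded before discontinuation, and Appendix 1 has a premature-discontinuation column that may yield one more assessment. Weighting corrects removal that is at random given observed data. Someone who would have missed the visits anyway is missing with or without the rule. All of this stands.

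**Conclusion.** The point holds as an internal conflict with a consequence for estimation. Section 9.2.3, read as written, cannot be followed together with Sections 3.2.6, 6.2, 7.3, 7.4.1, 9.1 and 11.2, and following it stops outcome collection on which the intention-to-treat, treatment-policy analysis depends. This part needs no assumption.

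Two stronger inferences are not supported: that removals will occur mostly in IMPACT, and that the resulting bias will favour IMPACT. The first depends on sites treating missed sessions as noncompliance. The second depends also on the removed having a higher CAS rate that weighting fails to recover. The range of about 0.96 to 0.85 for a true ratio of 1.00 is an upper-end illustration for the removal rates and multipliers assumed; it is not an estimate. The loss of power is small under the same kind of assumption.

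**What to change.** Amend 9.2.3 so that it agrees with 3.2.6, 6.2, 7.3, 7.4.1, 9.1 and 11.2. For randomized participants, noncompliance with sessions or assessments would be recorded as an adherence variable and would not by itself be a reason to end outcome collection at Months 4, 8 and 12. If the term is kept for any other purpose, define it.

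The change should be confined to outcome collection. It should leave untouched withdrawal of consent, the safety and best-interest grounds in 9.2.3, the undue-risk ground in 3.2.3, the pre-randomization rule in 3.2.4 and the suspension during incarceration in 15.3. An instruction to offer visits to everyone who has not withdrawn consent would be too broad, because it would override several of these.

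The cost is a short amendment and a note to sites. No visits are added to the schedule, and Section 9.1 already asks staff to pursue people who miss one. Because 9.2.3 already requires the reason for discontinuation to be recorded, any removals on this ground before the amendment can be counted by arm and reported.

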9.3 Participant Replacement

In cases of premature discontinuation, a replacement participant may be enrolled.

9.4 Participant Compensation

Participants will be compensated for each intervention visit and study visit with the amount as indicated in the SC-specific ICF as approved by Sterling IRB and the local IRB at the SC, where required. SCs will be encouraged to provide compensation commensurate with the time and effort required by the protocol and as per IRB guidelines.

9.5 Mitigation Plans for Social Harms

All SCs have specific policies governing the protection of human subjects. Medical and psychological assistance will be available in the immediate environment in the event a participant experiences any social harm resulting from participation in the study.

Measures to ensure safety will be taken if, at any time during the study, a participant divulges that they are at risk for harm, including being abused or experiencing violence, if harm is suspected or likely, or if the participant states they are suicidal/homicidal. Reporting will be done as appropriate to the situation and the legal statutes, including reporting to child protection agencies or other appropriate agencies, and referrals will be provided to appropriate support, counseling, or treatment resources. Social harms will be reported to the Protocol Team following the procedure for social harms reporting (see Section 12).

9.6 ATN QNS

The ATN QNS, established for notifications and queries from the ATN SCs to the Protocol Team, will be used for this study. SC study staff will use the ATN QNS to consult with the Protocol Team on any issues that may arise during study implementation, such as, but not limited to, participant management, study management, and safety reporting guidance. The ATN QNS is accessible via the ATN website (https://www.atnconnect.org). Upon receipt of a query, the

Protocol Team will discuss it as needed and formulate a response. The Protocol Team will respond to queries generally within 2 business days. If the Protocol Team anticipates that a response will take more than 2 business days to formulate, the Study Manager will inform the query requestor by email. Queries and responses will automatically be archived at the OCC. The Study Manager will post queries and responses deemed relevant to all SCs as Frequently Asked Questions on the ATN website, where they will be available to all SCs and the Protocol Team for future reference. Note that social harm/AE notification via the QNS does not meet the requirements to enter social harm/AE data in the EDC system.

10. Study Termination/Halting

